### 6.1.3. Pregnancy and breastfeeding

All female subjects with childbearing potential (they have at least one period during the last 12 months), must at V1 confirm that they are not pregnant or breastfeeding. A urine pregnancy test will be performed with a dipstick at site for confirmation. They will also be informed that no pregnancy is allowed during the investigation.

If the subject becomes pregnant during the investigation, it is important, that the subject informs the investigator or delegate immediately.

### 6.2. Recruitment and enrolment

Recruitment of potential subjects will begin once approval have been obtained from the Ethics Committee (EC). It is estimated that the recruitment process will be completed within 6 months.

**Table 4: Overview of the recruitment process**

Recruitment method	Outpatient clinic/hospital	Advertising	Coloplast Database
Potential subjects	
Recruitment will go through the outpatient clinic at the hospital site. Potential subjects are identified by the following searching criteria:
 
 
• <math>\geq 18</math> years of age
 
• Use clean intermittent catheterization to greatest extent possible (at least three times daily) for at least the last 1 month prior to inclusion
 
• Self-catheterize using a single use hydrophilic coated catheter for at least 1 month prior to inclusion
 
• Ability and willingness to participate in a 4-week study period
 
	
Recruitment will go through an advertisement in relevant magazines. In the advertisement the following searching criteria are stated:
 
 
• <math>\geq 18</math> years of age
 
• Use clean intermittent catheterization to greatest extent possible (at least three times daily) for at least the last 1 month prior to inclusion
 
• Self-catheterize using a single use hydrophilic coated catheter for at least 1 month prior to inclusion
 
• Ability and willingness to participate in a 4-week study period
 
 
In the advertisement potential subjects are asked to contact the coordinating PI for further information.
	
Recruitment will go through Coloplast Database and assessing potential subjects are identified by the following searching criteria:
 
 
• <math>\geq 18</math> years of age
 
• Use intermittent self-catheterization.
 

First contact	
The potential subjects will be contacted by mail, phone call or contacted during a planned visit in the outpatient clinic at the hospital.
 
If a subject is eligible and interested in participating in the investigation upon a short introduction, then written information about the investigation (Subject Information Form /Informed Consent Form) will be distributed to the subject.
 
The Principal Investigator or delegate will invite the subject to a Screening Visit (VO).
	
The potential subjects will mail or call the Coordinating Principal Investigator.
 
If a subject is eligible and interested in participating in the investigation upon a short introduction, then written information about the investigation (Subject Information Form /Informed Consent Form) will be sent to the subject and the subject will be re-directed to a recruiting site near the subjects' home for a potential Screening Visit (VO).
	
Potential subjects from the database will be contacted by phone or mail by the Principal Investigator or delegate.
 
If subjects are eligible and interested in participating upon a short introduction, then written information about the investigation (Subject Information Form /Informed Consent Form) will be sent to the subject before a potential Screening Visit (VO).

Recruitment method	Outpatient clinic/hospital	Advertising	Coloplast Database
Screening Visit (V0)	
At the scheduled Screening Visit (V0) the Principal Investigator or delegate will introduce the investigation and review the inclusion and exclusion criteria.
 
If the subject wishes to reconsider his/her participation at V0, the subject has the rights to wait minimum 24 hours before deciding on participation. If the subject hereafter decides to participate in the clinical investigation a Baseline Visit (V1) will be scheduled unless performed the same day as the Screening Visit. The Screening Visit can be formed at the site or as a phone call.
 
If the subject does not meet the inclusion criteria or meet the exclusion criteria, this will be registered at the Subject Pre-Screening Log.
	
At the scheduled Screening Visit (V0) the Principal Investigator or delegate will introduce the investigation and review the inclusion and exclusion criteria.
 
If the subject wishes to reconsider his/her participation at V0, the subject has the rights to wait minimum 24 hours before deciding on participation. If the subject hereafter decides to participate in the clinical investigation a Baseline Visit (V1) will be scheduled unless performed the same day as the Screening Visit.
 
The Screening Visit can be formed at the site or as a phone call.
 
If the subject does not meet the inclusion criteria or meet the exclusion criteria, this will be registered at the Subject Pre-Screening Log.
	
At the scheduled Screening Visit (V0) the Principal Investigator or delegate will introduce the investigation and review the inclusion and exclusion criteria.
 
If the subject wishes to reconsider his/her participation at V0, the subject has the rights to wait minimum 24 hours before deciding on participation. If the subject hereafter decides to participate in the clinical investigation a Baseline Visit (V1) will be scheduled unless performed the same day as the Screening Visit.
 
The Screening Visit can be formed at the site or as a phone call.
 
If the subject does not meet the inclusion criteria or meet the exclusion criteria, this will be registered at the Subject Pre-Screening Log.

Baseline Visit (V1)	If the subject decides to participate and it is certain that it is understood what the investigation entails, the subject will be asked to sign the SIF/ICF. When the SIF/ICF is signed the subject is considered included in the investigation.	If the subject decides to participate and it is certain that it is understood what the investigation entails, the subject will be asked to sign the SIF/ICF. When the SIF/ICF is signed the subject is considered included in the investigation.	If the subject decides to participate and it is certain that it is understood what the investigation entails, the subject will be asked to sign the SIF/ICF. When the SIF/ICF is signed the subject is considered included in the investigation.

### 6.3. Subject withdrawal criteria

The subject is allowed to withdraw from the investigation at any time for whatever reason without any consequences for their future treatment outside the clinical investigation. The Investigator may withdraw a subject from the investigation at any time if they judge it to be the subject's interest.

The investigator must withdraw a subject from the investigation due to:

- Major noncompliance with the CIP impacting the scientific integrity of the investigation
- If subject's safety and wellbeing is compromised by further participation
- Subjects lost to follow-up. At least three documented attempts will be made to verify subjects lost to follow-up

All replacements can be made by sponsors decision and site must contact the Clinical Manager for replacement of a subject.

A subject who is withdrawn from the investigation, for any reason, will be encouraged to contact the investigator if problems arise that the subject believes are related to the clinical investigation. Subjects who have not experienced any adverse events will not be followed up.

For subjects who experience adverse events, see Section 18.1.

If a subject shows symptom(s) of UTI, as judged by the investigator, after the subject has been included in the investigation, the subject must be examined and treated according to sites standard of care or advised by investigator or GP. If antibiotic treatment is needed the subject must be withdrawn from the investigation and Termination Visit (V5) performed as soon as possible.

The subject must be advised to stop using the reusable catheter (CLINY Self-Catheterization Set) PRIOR to start of the antibiotic treatment. The subject must also be advised to save the CLINY catheter in the CLINY Self-Catheterization set and bring it to site for the Termination Visit.

The subject can return for a new scheduled visit V1 in cases where an UTI is detected after inclusion but prior to start of the test period with CLINY Self-Catheterization Set. The subject must be terminated as a screening failure and can be enrolled as a new subject when the UTI is treated, and the subject fulfils the in- and exclusion criteria.

If a subject decides to discontinue prior to day 14 on re-use catheter (day 14 counted from day of Baseline V1), a replacement of the subject must follow. All replacements of subjects must be agreed with sponsor.

#### **6.4. Point of enrolment**

A subject is considered enrolled in the investigation when the written informed consent is obtained. The expected duration for each subject is described in Section 5.1 General.

#### **6.5. Subject Identification and Confidentiality**

Subjects will be identified in the eCRF and any other document transmitted to the sponsor by the Principal Investigator or delegate, by a unique identification number.

Data entered in the eCRF are confidential and will only be available to the sponsor (including sponsor delegates), members of data management teams, the statistician, members of the EC and if requested to regulatory authorities. The Principal Investigator (PI) will maintain as part of the investigational file a list identifying all subjects entered in the clinical investigation.

### **7. Procedures**

#### **7.1. Clinical investigation-related procedures and assessments**

##### **Screening Visit (V0), Week 0:**

- Introduction to the investigation and review of Informed Consent Form/Subject Information Form
- Check of in- and exclusion criteria
- Scheduling Baseline Visit (V1) within 3 days unless performed the same day as Screening visit (V0)
- Register the potential subject on the Pre-screening Log if not already registered

##### **Baseline Visit (V1), Week 0: Day 0**

- Introduction to the investigation reviewed and confirmed
- Informed Consent signed
- Check of in- and exclusion criteria
- Urine dipstick for hematuria, leucocytes, and nitrite level (Appendix F and G)
- For female subjects of childbearing potential: urine pregnancy dipstick
- Enrolment in the investigation and allocation of subject number
- Collect Baseline information:
  - Gender (male/female)
  - Age (at time of enrolment in years)
  - Height (in cm)
  - Weight (in kg)
  - Reason for using intermittent catheterization
  - When did you start using a catheter? (months/years)
  - Current single use catheter: brand/material/product/item number (at time of enrolment)
  - Single use catheter size at time of enrolment
  - Average number of catheters used per day during the last 1 month
  - Time spent on each catheterization from preparation to storage/disposal (in minutes)

- What is your handedness?
  - Right-handed
  - Left-handed
  - Mixed or cross-dominant (i.e., changes according to task)
  - Ambidextrous (i.e., equal ability in both hands)
- What is your urethral sensation?
  - Normal
  - Impaired
  - Hypersensitive
  - None
- What is your hand dexterity (left/right)?
  - Left hand:
    - Normal dexterity
    - Reduced dexterity
    - Greatly reduced dexterity
    - Don't know
  - Right hand:
    - Normal dexterity
    - Reduced dexterity
    - Greatly reduced dexterity
    - Don't know

- Review of concomitant medication at time of enrolment
- Instruct the subject in completing the Baseline questionnaires for evaluation of single use catheter:
  - ISC-Q assessment (paper) (Appendix B)
  - InCaSa assessment (paper) (Appendix C)
  - Perception assessment (paper) (Appendix D)
- Distribution of CLINY Self-Catheterization Set and investigational supplies
- Instruct the subject in use of CLINY according to the IFU (Appendix A)
- Instruct the subject in use of weekly urine dipstick form
- Insurance of subjects' compliance with the CIP
- Scheduling Phone Call Visit (V2) in Week 1, 7 days +/- 1 day after Baseline Visit (V1)
- Complete eCRF

#### **Phone Call Visit (V2), Week 1: Day 7 (+/- 1 day)**

- Review of Adverse events/Serious adverse events/Adverse device events, Device deficiencies and Protocol Deviations
- Review of changes in concomitant medication
- Reminder of instruction for CLINY Self-Catheterization Set
- Evaluation of catheterization since last visit:
  - Have the subject used single use catheters since Baseline Visit
  - Did the subject follow all cleaning procedures stated in the IFU?
  - Average number of daily catheterizations with CLINY the subject completed since Baseline Visit
  - Average time spent on each catheterization from preparation to storage/disposal (in minutes)
- Urine dipstick for hematuria, leucocytes, and nitrite level performed on day of call (weekly urine dipstick form) (Appendix G)
- Remind subject of ending use of CLINY catheter after the test period regardless scheduled date of Visit 5
- Insurance of subjects' compliance with the CIP
- Scheduling Phone Call Visit (V3) in Week 2, 14 days +/- 1 day after Baseline Visit (V1)
- Complete eCRF

#### **Phone Call Visit (V3), Week 2: Day 14 (+/-1 day)**

- Review of Adverse events/Serious adverse events/Adverse device events, Device deficiencies and Protocol Deviations
- Review of changes in concomitant medication
- Reminder of instruction for CLINY Self-Catheterization Set
- Evaluation of catheterization since last visit:
  - Have the subject used single use catheters since last Phone Call Visit
  - Did the subject follow all cleaning procedures stated in the IFU?
  - Average number of daily catheterizations with CLINY the subject completed since Phone Call Visit
  - Average time spent on each catheterization from preparation to storage/disposal (in minutes)
- Urine dipstick for hematuria, leucocytes, and nitrite level performed on day of call (weekly urine dipstick form) (Appendix G)
- Remind subject of ending use of CLINY catheter after the test period regardless scheduled date of Visit 5
- Insurance of subjects' compliance with the CIP
- Scheduling Phone Call Visit (V4) in Week 3, 21 days +/-1 day after Baseline Visit (V1)
- Complete eCRF

#### **Phone Call Visit (V4), Week 3: day 21 (+/-1 day)**

- Review of Adverse events/Serious adverse events/Adverse device events, Device deficiencies and Protocol Deviations
- Review of changes in concomitant medication
- Reminder of instruction for CLINY Self-Catheterization Set
- Evaluation of catheterization since last visit:
  - Have the subject used single use catheters since last Phone Call Visit
  - Did the subject follow all cleaning procedures stated in the IFU?
  - Average number of daily catheterizations with CLINY the subject completed since Phone Call Visit
  - Average time spent on each catheterization from preparation to storage/disposal (in minutes)
- Urine dipstick for hematuria, leucocytes, and nitrite level performed on day of call (weekly urine dipstick form (Appendix G)
- Remind subject of ending use of CLINY catheter after the test period regardless scheduled date of Visit 5
- Insurance of subjects' compliance with the CIP
- Remind the subject to bring (weekly urine dipstick form) at Termination Visit
- Scheduling Termination Visit (V5) in Week 4, 28 days +/- 3 days after Baseline Visit (V1)
- Complete eCRF

#### **Termination Visit (V5), Week 4: Day 28 (+/3 days)**

- Review of Adverse events/Serious adverse events/Adverse device events, device deficiencies and Protocol Deviations
- Review of changes in concomitant medication
- Evaluation of catheterization since last visit:
  - Have the subject used single use catheters since last Phone Call Visit
  - Did the subject follow all cleaning procedures stated in the IFU?
  - Average number of daily catheterizations with CLINY the subject completed since Phone Call Visit

- Average time spent on each catheterization from preparation to storage/disposal (in minutes)
- Instruct the subject in completing the Termination questionnaires for evaluation on the test period with reuse catheter, CLINY Self-Catheterization set:
  - ISC-Q assessment (paper) (Appendix B)
  - InCaSa assessment (paper) (Appendix C)
  - Perception assessment (paper) (Appendix D)
- Preference: (See Appendix E)
  - Catheter preferred (paper)
  - Reason for preference (paper)
  - Consideration to switch to a reusable catheter in the future (paper)
- Reason for drop out if Termination Visit is performed prior to 28 test days
- Urine dipstick for hematuria, leucocytes, and nitrite level (Appendix F & G)
- Review of weekly urine dipstick form for completeness and compliance.
- Ensure of the subjects' wellbeing and compliance with the CIP
- Collect CLINY Self-Catheterization Set. The catheter should be stored in the catheter case WITHOUT Milton solution
- Send CLINY Self-Catheterization set for Laboratory assessments and analysis
- Perform device accountability
- Complete eCRF

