### **5. Design of the clinical investigation**

#### **5.1. General**

The investigation is designed as an open-labelled, single-arm investigation, in which the reuse CLINY catheter will be compared to single use catheters at baseline.

The study design includes an initial evaluation of a cohort of catheter users who currently practice hydrophilic single use clean intermittent catheterization. The cohort will be followed for 4 weeks (28 days) when switching to multiple reuse catheters.

The test period of 4 weeks will consist of up to 3 site visits and 3 phone visits within a 4-week test period. Subjects using single use catheters for bladder management will use one distributed CLINY Self-Catheterization Set during the test-period. The expected duration of the total test-period is 28 days.

In total, 40 subjects will be included in the investigation. Each subject will undergo a Screening Visit (V0), a Baseline Visit (V1), 3 phone calls (V2, V3 and V4) and a Termination Visit (V5) carried out by the Principal Investigator (PI), or delegate. Visit 0 and 1 can be performed on the same day.

At a scheduled Screening Visit (V0), the subject will be verbally informed about the investigation, where the PI or delegate will give information about the investigation, the content and what it involves when participating in the investigation and the eligibility criteria. This information can be performed as a phone call if needed and the subject will be distributed a Subject Information Form/Informed Consent Form/ (SIF/ICF) by mail.

At the scheduled Baseline Visit (V1), the subject receives additional information if needed and the in- and exclusion criteria will be reviewed. See section 6.2 for recruitment and enrolment.

The Screening Visit (V0) and Baseline Visit (V1) can be performed the same day.

If the subject wishes to reconsider his/her participation at V0 after another oral review of the content of the investigation, the subject has the rights to wait minimum 24 hours before deciding on participation. If the subject hereafter decides to participate in the clinical investigation a V1 will be scheduled unless performed the same day as the Screening Visit (V0).

The subject is included in the investigation upon signed informed consent at the Baseline visit (V1). The Baseline Visit (V1) can be conducted at the latest, 3 days after V0.

At V1, all baseline information will be collected by the PI or delegate (see flow chart, Table 5).

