### 5.4. Rationale for selection and measurement of endpoints

The primary as well as part of the exploratory endpoints and assessments are subjective and have been selected as they are considered essential parameters to evaluate the effects of repeated reuse of catheters and for the observation on the impact of a switch from single use to reusable catheters.

To evaluate the primary endpoint HR-QoL, the ISC-Q questionnaire will be applied. The ISC-Q is a newly developed and validated patient reported outcome questionnaire that evaluates aspects of quality of life specific to the needs of patients with neurogenic bladder disorders who perform CIC. The questionnaire consists of 24 items categorized in 4 domains, including ease of use, convenience, discreetness, and psychosocial well-being. Each item is rated on a 5-point Likert scale.

The secondary as well as part of the exploratory endpoints are objective and are essential to investigate the effects of repeated reuse of catheters and for the observation on the impact of a switch from single use to reusable catheters as well as to ensure safety.

To evaluate the exploratory endpoint, satisfaction of intermittent catheterization, the InCaSa Questionnaire will be applied (InCaSa-Intermittent Catheterization Satisfaction Questionnaire).

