## 7.2. Flow-chart

Table 5: Flow chart showing the connection between visits, assessments, and procedures

	PER-FORMED BY	SCREENING VISIT	BASELINE VISIT	PHONE CALL VISIT	PHONE CALL VISIT	PHONE CALL VISIT	TERMINTION VISIT
VISIT	-	V0	V1	V2	V3	V4	V5
WEEK	-	WEEK 0	WEEK 0	WEEK 1	WEEK 2	WEEK 3	WEEK 4
VISIT WINDOW	-	-	-3DAYS	±1 day 7 DAYS	±1 day 14 DAYS	±1 day 21 DAYS	+3 days 28 DAYS
GENERAL							
Introduction to the investigation and review of Informed Consent Form/Subjects Information Form	Investigator or delegate	X					
Check of in- and exclusion criteria	Investigator or delegate	X	X				
Informed Consent Signed	Investigator and Subject		X				
Allocation of subject number	Investigator or delegate		X				
Collect Baseline information	Investigator or delegate		X				

	PER-FORMED BY	SCREENING VISIT	BASELINE VISIT	PHONE CALL VISIT	PHONE CALL VISIT	PHONE CALL VISIT	TERMINITION VISIT
Review of concomitant medication	Investigator or delegate		X	X	X	X	X
Assess AEs/ADEs/SAEs/SADES, Device Deficiencies and Protocol Deviations	Investigator or delegate		X	X	X	X	X
QUESTIONNAIRES AND ASSESSMENTS							
ISC-Q assessment	Subject		X				X
InCaSa assessment	Subject		X				X
Perception assessment	Subject		X				X
Evaluation of catheterization since last visit	Subject			X	X	X	X
Preference	Subject						X
Reason for drop out if Termination Visit is performed prior to 28 test days	Subject						X
PROCEDURES							
Urine dipstick for haematuria, leucocytes, and nitrite	Investigator or delegate		X				X
Urine dipstick for hematuria, leucocytes, and nitrite	Subject			X	X	X	
Urine dipstick (female subjects of childbearing potential)			X				
Remind subject of ending use of CLINY catheter after 28 days of use regardless scheduled date of Visit 5	Investigator or delegate			X	X	X	
Reminder of instruction for CLINY Self-Catherization set	Investigator or delegate			X	X	X	
Insurance of subject's compliance with CIP	Investigator or delegate		X	X	X	X	X
Instruct the subject in use of weekly urine dipstick form	Investigator or delegate		X				
Review of weekly urine dipstick form for completeness and compliance							X

	PER-FORMED BY	SCREENING VISIT	BASELINE VISIT	PHONE CALL VISIT	PHONE CALL VISIT	PHONE CALL VISIT	TERMINTION VISIT
Instruct the subject in use of CLINY accordingly the IFU	Investigator or delegate		X				
Distribution of CLINY Self-Catheterization set and investigational supplies	Investigator or delegate		X				

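### The order of the ISC-Q relative to staff questioning is not fixed at V1 or V5, and the single-use and cleaning questions listed before it at V5 have no V1 counterpart

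*Combined protocol and SAP*

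**What the plan says.** Section 5.1 describes an "open-labelled, single-arm investigation, in which the reuse CLINY catheter will be compared to single use catheters at baseline". Section 5.4 states that "The primary as well as part of the exploratory endpoints and assessments are subjective". Section 10.3 analyses the ISC-Q index score by catheter and concludes an effect if the 95% confidence interval for the difference excludes zero. Since single use is rated at V1 and reuse at V5, that difference is the change between the two visits.

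For V5, the list in section 7.1 opens with "Review of Adverse events/Serious adverse events/Adverse device events, device deficiencies and Protocol Deviations". Concomitant medication follows, and then the evaluation of catheterization since the last contact. That evaluation asks about use of single use catheters, "Did the subject follow all cleaning procedures stated in the IFU", the daily number of catheterizations and the time each takes. Next comes "Instruct the subject in completing the Termination questionnaires for evaluation on the test period with reuse catheter, CLINY Self-Catheterization set", then preference, and later the dipstick.

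For V1, the list gives consent, the eligibility check, the dipstick, subject-number allocation, the baseline questions and concomitant medication. It then gives "Instruct the subject in completing the Baseline questionnaires for evaluation of single use catheter", and only afterwards the hand-out of CLINY.

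The flow chart in 7.2 marks "Assess AEs/ADEs/SAEs/SADES, Device Deficiencies and Protocol Deviations" at V1 as well as at V2 to V5. It marks the catheterization evaluation at V2 to V5 only, in a row below the ISC-Q, InCaSa and perception rows. Sections 5.1 and 11.1 say that the subject completes the questionnaires on paper and that site personnel enter them.

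**The concern.** When an open-label trial measures a self-rated outcome twice and subtracts, the two ratings should be taken under conditions as alike as practicable. If a site works down the V5 list, the subject has just been asked about problems with CLINY and about adherence to its cleaning routine before rating life with it. No single-use or cleaning question comes before the baseline rating.

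The questioning overlaps with what is scored. Table 6 lists stinging and pain during catheterization as a likely device effect. ISC-Q item 4 asks about discomfort on insertion, and item 24 about worry over long-term problems. Questioning could lower the rating by recalling problems, or raise it if the subject wishes to appear content and compliant. Either way the effect would sit in V5 and could not be separated from the catheter effect in the 10.3 analysis. If the order is simply left open, sites in this multi-site trial may also differ.

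**Working it through.** **Step 1: compare the order of items.**

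| Item | 7.1 list, V1 | 7.1 list, V5 | Flow chart 7.2 |
|---|---|---|---|
| AE, deficiency and deviation review | not listed | before ISC-Q | row above ISC-Q; marked V1 to V5 |
| Single-use and cleaning questions | not listed | before ISC-Q | row below ISC-Q (within the catheterization evaluation); marked V2 to V5 |
| Frequency and time per catheterization | before ISC-Q (baseline questions) | before ISC-Q | V1: within baseline information, row above ISC-Q; V2 to V5: within the catheterization evaluation, row below ISC-Q |
| Urethral sensation, dexterity | before ISC-Q | not listed | within baseline information |
| Dipstick | before ISC-Q | after ISC-Q | row below the questionnaires |

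Three things follow.

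- The 7.1 list and the flow chart place the catheterization evaluation on opposite sides of the ISC-Q at V5.
- The 7.1 list and the flow chart disagree on whether an AE review takes place at V1.
- The single-use and cleaning questions have no V1 counterpart in either place. The frequency and time questions do.

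No section declares the bullets or the rows to be a sequence, and none requires the ISC-Q to come first.

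**Step 2: the plan's own figure.** Section 6 gives a minimum of 20 completers and 50% drop-out: 20 / (1 - 0.5) = 40 enrolled, which reproduces. The plan gives no power, SD or effect size, so there is nothing further to reproduce. The range of 20 to 40 completers is used below.

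**Step 3: what a shift would do under the 10.3 rule (illustration).** With two complete visits per subject, the mixed model is equivalent to a paired t-test. Let b be an assumed shift in units of the SD of the V5-V1 difference, with no true catheter effect and two-sided alpha 0.05 (section 10.6). The chance that the interval excludes zero is P(|T| > t(0.975, n-1)), where T is noncentral t with n-1 degrees of freedom and noncentrality b times the square root of n.

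| n | b = 0 | 0.1 | 0.2 | 0.3 | 0.5 | CI half-width, in SD |
|---|---|---|---|---|---|---|
| 20 | 5.0% | 7.1% | 13.6% | 24.7% | 56.5% | 0.47 |
| 40 | 5.0% | 9.5% | 23.5% | 45.7% | 86.9% | 0.32 |

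The half-width is t(0.975, n-1) divided by the square root of n. The values of b are assumptions. The documents supply none, and the table would be the same for a bias of this size from any other source.

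**The case against.** A reader might infer something stronger: that the plan prescribes a compliance interview before the V5 rating, in a context wholly absent at V1, and that this moves the result. The documents do not support that, for these reasons.

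- **No sequence is declared.** Completing the eCRF is the last bullet at V1 to V5, although section 11.1 prefers immediate entry, so the bullets are not strictly steps in time. The flow chart is no better guide to order: it is grouped by type, and scheduling of V1 stands below the V1 procedures. The 7.1 lists run broadly from consent to close-out, and a site could reasonably follow them. Even so, the most that can be said is that the order is unspecified.
- **V1 is not free of questioning.** The flow chart and Appendix H mark AE assessment at V1, and the 7.1 list puts several questions on catheterization before the baseline ISC-Q. What stands is a difference in content. AEs count only from consent (section 5.6) and CLINY is handed out after the baseline forms, so a V1 review has almost nothing to cover.
- **Who asks is not settled.** The flow chart assigns the catheterization evaluation to the subject, and Appendix H to subject and site. The ISC-Q is self-completed on paper, which limits direct interviewer influence but not the effect of what was discussed just before.
- **The same topics come up at V2, V3 and V4.** Reordering V5 therefore removes only same-day prompting. A subject who stops because of an infection attends V5 because of that event, in whatever order the items are taken.

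It is also fair to say that sections 3.2 and 10.7 set no formal success criterion. Section 10.3 nevertheless keeps a significance rule, so an avoidable shift still matters.

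**Conclusion.** The point holds in a limited form. The order is open at both visits, the 7.1 list and the flow chart differ at V5, and two of the four V5 catheterization questions have no baseline counterpart. With a subjective, open-label V1-V5 difference as the primary result, same-day questioning could enter it.

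Its size and direction cannot be obtained from the documents. The percentages show only that a shift of 0.1 to 0.3 SD would not be negligible under the 10.3 rule. They rest on an assumed shift, complete pairs and a zero catheter effect, and are not evidence that bias will occur.

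This is an inexpensive improvement and not a flaw that undermines the trial. Catheter and visit remain fully confounded in this single-arm design, and the effect of questioning at V2 to V4 remains as well.

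**What to change.** State in section 7.1 that the listed order applies to the questionnaires, and set it as follows.

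- **V5:** the subject completes the paper ISC-Q, InCaSa, perception and preference forms, and hands them in, before any AE, deviation, compliance or dipstick item.
- **V1:** the subject completes the ISC-Q, InCaSa and perception forms directly after consent, the eligibility check and subject-number allocation, and before the dipstick and the baseline interview.

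Align the V1 and V5 lists with the flow chart, and settle whether an AE review takes place at V1 and, if so, place it after the forms.

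The cost is a small change in visit flow. Number allocation at V1 has to move ahead of the dipstick so that the forms carry a subject number. Forms, visits and sample size do not change, and no data are lost.
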